9.4 Statistical Analysis

9.4.1 Demographic and Baseline Characteristics

Demographics and baseline characteristics will be summarized using descriptive statistics for continuous variables, and frequencies and percentages for categorical variables.

9.4.2 Safety Analyses

The safety endpoints will include:

- Incidence of DLTs
- Incidence of AEs and related AEs
- Incidence of grade 3 and grade 4 AEs
- Incidence of SAEs and death
- Laboratory values
- ECG/vital signs

The safety endpoints will be listed and/or summarized by dose cohort. No inferential statistical analyses will be performed.

The analyses of safety will be based on the frequency of adverse events and their severity for patients in each portion who received at least one dose of study treatment. Worst toxicity grades per patient will be tabulated for select adverse events and laboratory measurements by using NCI CTCAE criteria v5.0.

9.4.3 Efficacy analyses

The efficacy endpoints will include:

- ORR: The percentages of CR, CR+PR, and CR+PR+SD as well as Conversion Rate for Group 2 will be presented, as will the median duration of response. The 95% confidence intervals of these percentages may also be presented.
- DOR: DOR is defined as time from the initial response to documented disease progression. This variable will be analyzed via Kaplan-Meier methodology.

Additional analyses may also be performed as appropriate.

These analyses will be performed from time to time for presentation/publication purposes.

9.4.4 Pharmacokinetic Analyses

The PK parameters (e.g. $AUC_{(0-\infty)}$, $AUC_{(0-t)}$, C_{max} , t_{max} , λ_z , and $t_{1/2}$) will be assessed by analysis of Tenalisib and its metabolite; and Romidepsin plasma concentrations during the dose escalation phase of the study. These variables will be summarized by n, mean (both arithmetic and geometric if applicable), standard deviation, median, minimum, and maximum by dose.

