3.1.2 Secondary Endpoints

- **Efficacy:**

1. **Objective Response Rate (ORR)**, defined as sum of CR and PR rates, assessed according to the Lugano Classification for initial evaluation, staging, and response assessment of Hodgkin/non-Hodgkin lymphoma in PTCL patients; and according to the modified Severity Weighted Assessment Tool (mSWAT) in CTCL patients.
2. **Duration of Response (DoR)**, calculated as time from the initial response to documented disease progression.

- **Pharmacokinetics:**

PK Parameters [AUC $(0-\infty)$, AUC $(0- t)$, C_{max} , t_{max} , K_{el} , and $t_{1/2}$] of Tenalisib and Romidepsin.

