3.2.1 Phase I: Dose Escalation

3.2.1.1 Dose Escalation Cohorts

Sequential dose escalation will begin with Cohort 1. A minimum of three patients will be enrolled at each dose level. Dose levels will be increased in successive increments according to the dose escalation cohorts mentioned in Table 1. Escalation to the next cohort will occur if no patient within a three-patient cohort or one in six patients experiences a dose limiting toxicity (DLT). De-escalation to different lower doses in case of DLT criteria met will be done as per the discretion of the Safety Review Committee (SRC). The highest doses of the combination (Tenalisib at 800 mg BID plus Romidepsin IV 14 mg/m²) will be considered as optimal in case there is no DLT at this dose level.

Table 1: Dose Escalation Scheme

Cohort	N	Tenalisib ¹	Romidepsin ²
Cohort 1	3-6	Tab. 400 mg PO twice a day	IV 12 mg/m ² on Day 1, 8 and 15
Cohort 2	3-6	Tab. 600 mg PO twice a day	IV 12 mg/m ² on Day 1, 8 and 15
Cohort 3	3-6	Tab. 800 mg PO twice a day	IV 14 mg/m ² on Day 1, 8 and 15

Note: Alternate dose levels/dosing schedules may be considered by the SRC if deemed essential based on emerging safety and PK data.

¹*In case the dose (e.g. 800 mg BID) is leading to DLT of the combination, the dose of Tenalisib will be reduced to lower dose (e.g. 600 mg BID) and will be evaluated for safety in a separate cohort.*

²*In case the dose (e.g. 14 mg/m²) is leading to DLT of the combination, the dose of Romidepsin will be reduced to lower dose (e.g. 12 mg/m²) and if required further to 10 mg/m² and will be evaluated for safety in a separate cohort.*

Notes:

- For dose escalation decision, safety data of the first 28-days follow up and PK data of C1D1 and C1D8 is essential.
- The dose escalation may occur if no patient within a three-patient cohort experiences a DLT as defined in Section 7.6 If one of three patients within a 3-patient cohort experiences

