8. Chemistry Panel I must be done \leq 7 days prior to C1D1. However, if these initial examinations are obtained within 72 hours of C1D1; they do not have to be repeated. These tests will be performed at supplementary (unscheduled) visits if clinically indicated.
9. Chemistry Panel II must be done \leq 7 days prior to C1D1. However, if these initial examinations are obtained within 72 hours of C1D1; they do not have to be repeated. During treatment, the labs will be performed at C3D1 (\pm 1 days), C5D1 (\pm 1 days) and C8D1 (\pm 7 days) and/ or at the EOT. These tests will be performed at supplementary (unscheduled) visits if clinically indicated.
10. Serology includes HIV, HBV, HCV and CMV. Historical evidence in last 12 weeks is acceptable.
11. PT/INR: PT and INR test must be done \leq 7 days prior to C1D1. However, if initial examination is obtained within 72 hours of C1D1; this do not have to be repeated. In case of abnormality, additional tests including aPTT to be done as per investigator discretion. This test will be performed at supplementary visits if clinically indicated.
12. Pregnancy test is required for women of child bearing potential. A serum/urine pregnancy test will be performed at screening and C1D1 (within 72 hours) of dosing. Urine pregnancy test will be performed at other visits as indicated.
13. 12-lead ECG: PK matching ECG will be done on C1D1 and C1D8. Please refer ECG table for detailed time points. Additional ECGs will be obtained if clinically indicated. Triplicate ECGs will be performed to confirm the significant changes of single ECG. Refer Section 6.5.
14. PK: The blood will be collected for PK on following time points: C1D1: Pre-infusion (0), 1, 2, 3, 5, 7, 9, 10 hrs post-infusion. C1D8: Sampling with respect to Tenalisib dosing. Pre-dose (0), 0.5, 1, 2, 3, 4, 5, 6, 8, 10, 11 post-dose. Pre-dose sample will be taken on C2D1, C3D1 and C4D1. Patient will be hospitalized on C1D1 and C1D8 at the discretion of the site in order to facilitate multiple procedures (e.g. PK blood draws, ECGs) that required to be performed on C1D1 and C1D8. On C2D1, C3D1, C4D1, patients should consume their morning dose at the clinic after the pre-dose sample. Refer Section 6.10.

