15. A bone marrow biopsy: PTCL: Bone marrow biopsy should be collected \leq 12 weeks prior to C1D1 and/or to confirm a complete response to the study drug. If patient has negative bone marrow at baseline, there is no need to have it repeated to confirm CR. Additional biopsy will be obtained if clinically indicated. CTCL patients with predominantly blood involvement (B₂) will have a bone marrow biopsy at screening (unless it has been shown to be negative within the last 6 months) and as indicated to confirm a complete response.
16. Skin biopsy: In CTCL patients, skin biopsy should be performed at screening, and to confirm a complete response. Historical data of 12 weeks is acceptable.
17. Radiological scan: In PTCL and CTCL patients with nodal and visceral involvement, PET and “diagnostic quality” CT scan will be performed at the time of screening within 28 days of screening. Following screening, CT scans should be repeated at C3D1 (\pm 7 days), C5D1 (\pm 7 days) and C8D1 (\pm 7 days). PET should be done at C3D1 (\pm 7 days) and to confirm CR.
18. Skin assessment: In all CTCL patients, mSWAT will be performed at the time of screening within 28 days of screening and at C3D1 (\pm 7 days), C5D1 (\pm 7 days) and C8D1 (\pm 7 days). Disease response assessment will be performed at C3D1 (\pm 7 days), C5D1 (\pm 7 days) and C8D1 (\pm 7 days) and/ or at the EOT or as clinically indicated using mSWAT.
19. Skin photograph: In CTCL patients, skin lesion photograph will be taken at screening, at the time of response (PR/CR/PD) and at other time points as required by the PI.
20. Blood will be collected for biomarkers (e.g. sIL2R and CTACK for PTCL; CD30, IL-31 and IL-32 for CTCL).
21. Tenalisib will be administered orally twice a day from Day 3 (C1D3) onward in 28-days of cycle for 7 cycles in absence of disease progression or toxicity warranting discontinuation of therapy. On the day of Romidepsin administration, the morning dose of Tenalisib should be given in clinic one hour prior to Romidepsin infusion. Tenalisib will be dispensed at the start of each cycle (C1D1, C2D1, C3D1 ...). Only in Cycle 1, Tenalisib will be

given starting from Day 3 (i.e. C1D3). Patients will be, therefore, be instructed to start the treatment on C1D3 and will be informed that they will receive Tenalisib for 25 days in the first cycle.

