Appendix B: Contraceptive Guidelines and Pregnancy

Women Not of Childbearing Potential are defined as Follows
Women are considered post-menopausal and not of child bearing potential if they have had 12 months of natural (spontaneous) amenorrhea with an appropriate clinical profile (e.g. age appropriate, history of vasomotor symptoms) or six months of spontaneous amenorrhea with serum FSH levels > 40 mIU/mL] or have had surgical bilateral oophorectomy (with or without hysterectomy) at least six weeks ago. In the case of oophorectomy alone, only when the reproductive status of the woman has been confirmed by follow up hormone level assessment is she considered not of child bearing potential.
Contraceptive Guidelines for Women of Child-Bearing Potential
Women of child-bearing potential, defined as all women physiologically capable of becoming pregnant, must use highly effective contraception during the study and for 5 T1/2 (48 hrs) plus an additional 4 weeks after stopping treatment . The highly effective contraception is defined as either:

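### AUC(0-inf) is a listed Tenalisib endpoint, but the only serial profile is taken during twice-daily dosing, so it includes carry-over; AUC over the dosing interval is the measure to name (minor)

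*Protocol*

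**What the plan says.** **Parameters.** Protocol 3.1.2 makes AUC(0-inf), AUC(0-t), Cmax, tmax, Kel and t1/2 secondary endpoints for both drugs; its list ends "K_{el} , and $t_{1/2}$] of Tenalisib and Romidepsin". SAP 4.2 repeats it. Protocol 9.4.4 gives the same set as examples and says that they "will be assessed by analysis of Tenalisib and its metabolite; and Romidepsin plasma concentrations during the dose escalation phase of the study". None of the three places names AUC over the dosing interval.

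**Dosing and sampling in dose escalation.** Table 5, footnote 21: "Tenalisib will be administered orally twice a day from Day 3 (C1D3) onward in 28-days of cycle for 7 cycles". No PK sample is scheduled on C1D3. Footnote 14 sets the sampling days. On C1D1, when Romidepsin is given alone: "C1D1: Pre-infusion (0), 1, 2, 3, 5, 7, 9, 10 hrs post-infusion". Then: "C1D8: Sampling with respect to Tenalisib dosing. Pre-dose (0), 0.5, 1, 2, 3, 4, 5, 6, 8, 10, 11 post-dose". C2D1, C3D1 and C4D1 have a pre-dose sample only, and section 6.10 rules out PK in the expansion part.

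**Use.** For the escalation decision, section 3.2.1.1 says that "PK data of C1D1 and C1D8 is essential". SAP section 11 leaves PK analysis to a separate organization, whose plan is not among the documents.

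**Half-life.** Neither document states a Tenalisib half-life. Section 1.1.2 reports no accumulation at C2D1 in the earlier T-cell lymphoma study, and says that half-life changed with dose without giving figures. Appendix B sets contraception "for 5 T1/2 (48 hrs) plus an additional 4 weeks after stopping treatment".

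**The concern.** AUC(0-inf) describes exposure from one dose. It is the measured area plus a tail, the last concentration divided by the terminal rate constant. By the C1D8 morning dose a patient has had about ten earlier doses, so the last concentration, and hence the tail, contains residue from them. The quantity comparable with single-dose AUC(0-inf) is AUC over one dosing interval at steady state, which is not listed.

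The overstatement grows with half-life, so it need not be constant across patients or cohorts. If half-life differs between the 400, 600 and 800 mg cohorts, comparisons of AUC(0-inf) by dose would be distorted. It would also exaggerate an interaction. As an illustration with assumed values, if Romidepsin halved Tenalisib clearance and half-life went from 3 to 6 h, true exposure would double, but AUC(0-inf) from this profile would rise 2 x 1.333/1.067 = 2.5-fold. PK of the combination is a secondary objective, so the endpoint should be one that the sampling can deliver.

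**Working it through.** **Inputs.** Dosing interval tau = 12 h (twice daily, taken as even). Doses before the C1D8 morning dose: 2 x 5 days (C1D3 to C1D7) = 10. Last sample: 11 h. Mean AUC(0-t) at C1D1 and C2D1: section 1.1.2. The 48 h: Appendix B. Assumed: linear one-compartment kinetics and, for the oral calculation, an absorption rate of 1.5 per h.

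**1. The plan's own statement.** C2D1/C1D1 ratios of AUC(0-t) from section 1.1.2:
- 200 mg: 3985.52/3713.94 = 1.07
- 800 mg fed: 12737.21/13204.17 = 0.96
- 800 mg fasting: 13210.24/14033.67 = 0.94

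These agree with the reported lack of accumulation. The Cmax ratios are 1.22, 1.08 and 0.81.

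**2. Formula.** For a bolus at steady state, AUC(0-inf) from the profile divided by single-dose AUC(0-inf) is R = 1/(1 - 2^(-12/t1/2)). This is also the accumulation ratio. The oral figures below superpose the ten earlier doses and the C1D8 dose, then take AUC(0-11) + C(11)/k.

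**3. Results over a range of half-lives.**

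| t1/2 (h) | R, bolus | Ratio, oral | Share of AUC(0-inf) extrapolated | Half-lives in 11 h | AUC(0-11)/AUC(0-12) |
|---|---|---|---|---|---|
| 2 | 1.02 | 1.02 | 3% | 5.5 | 0.99 |
| 3.1 | 1.07 | 1.09 | 10% | 3.5 | 0.98 |
| 6 | 1.33 | 1.36 | 30% | 1.8 | 0.96 |
| 9.6 | 1.72 | 1.76 | 46% | 1.15 | 0.94 |
| 12 | 2.00 | 2.04 | 54% | 0.9 | 0.94 |

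AUC(0-12) at steady state divided by single-dose AUC(0-inf) is 1.00 in every row.

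**4. The two clues on half-life.**
- Section 1.1.2: the largest AUC ratio, 1.07, solves to t1/2 of about 3.1 h, an overstatement of 7% (bolus) to 9% (oral). The two ratios below 1 imply none.
- Appendix B: 48/5 = 9.6 h, an overstatement of 72% (bolus) to 76% (oral), with 11/9.6 = 1.15 half-lives observed.

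**5. Cross-check.** C1D1 AUC(0-t)/Cmax in section 1.1.2 is 3713.94/1463.57 = 2.5 h (200 mg), 14033.67/4174.71 = 3.4 h (800 mg fasting) and 13204.17/2988.66 = 4.4 h (800 mg fed). A one-compartment bolus with t1/2 of 9.6 h would give 7.6 h for sampling to 11 h, or 6.1 h for sampling to 8 h. The printed ratios correspond to half-lives of about 1.8 to 3.4 h and an overstatement of about 1 to 10%. This uses ratios of means and assumes that the earlier study sampled to at least about 8 h.

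**The case against.** The strongest reply is that the harm is small and partly covered already. The overstatement ratio is the accumulation ratio, and the protocol reports no accumulation. AUC(0-t) and Cmax are planned as well. Section 3.2.1.1 calls for PK data in general, not AUC(0-inf), and its escalation rules count DLTs. The list in 3.1.2 covers both drugs together, and AUC(0-inf) suits Romidepsin given alone on C1D1. The list in 9.4.4 is only by example, and the separate PK plan may already use AUC over the dosing interval.

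Most of this stands and limits the size and consequence. It does not make the parameter right. Protocol 3.1.2 and SAP 4.2 list AUC(0-inf) for Tenalisib without qualification, and nothing in the two documents says how it would be handled in a multiple-dose profile. If the PK plan does use AUC over the interval, the endpoint list should match it.

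A reader might infer four stronger things that the documents do not support:
- *That the overstatement is about 72%.* This rests on a contraception washout that may not refer to Tenalisib, and it conflicts with section 1.1.2. A slow terminal phase carrying little of the AUC could reconcile the two clues, but the 72% would still not follow.
- *That 11 h is too short for Kel and t1/2.* This holds near 9.6 h; at 3.1 h the window spans about 3.5 half-lives. Carry-over does not itself bias either parameter.
- *That escalation decisions will be misled.* They rest mainly on DLTs, and usable exposure measures remain.
- *That results cannot be compared with the earlier study.* That study reports AUC(0-t), which this trial also plans.

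**Conclusion.** The point holds as a minor mis-specification of a secondary endpoint. Under linear kinetics the direction is certain: AUC(0-inf) from the C1D8 Tenalisib profile exceeds exposure per dose. No single size should be asserted. The earlier study's data support about 0 to 10%; a 9.6 h half-life, if Appendix B means Tenalisib, would give about 72 to 76% and only then put Kel and t1/2 in doubt. AUC(0-t) to 11 h holds 94 to 99% of the 12 h interval AUC across half-lives of 2 to 12 h, so a usable exposure measure survives. The figures assume one compartment, an even 12 h interval and, for the oral case, the stated absorption rate.

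**What to change.** In protocol 3.1.2 and 9.4.4, SAP 4.2 and the separate PK plan:

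- Replace AUC(0-inf) for Tenalisib at C1D8 with steady-state AUC over the dosing interval (0 to 12 h).
- Obtain the 12 h value by extrapolation from the last samples. Use the pre-dose sample only where recorded dose times show a preceding interval of about 12 h. Section 3.4.3.1 ties doses to meals such as breakfast and dinner, so the overnight interval may exceed 12 h and the pre-dose value may then be lower than the true 12 h value. The area to be added after 11 h is only about 1 to 6% of the total.
- Keep AUC(0-inf) for Romidepsin. Keep AUC(0-t), Cmax, tmax and the C2D1 to C4D1 troughs for Tenalisib.
- Report Tenalisib Kel and t1/2 only where the data support the terminal slope.

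The cost is wording and a check of dose times, with no new samples or visits. The downside is that half-life may be missing for some patients.

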9.4.5 Exploratory Analysis

The analyses of correlative markers are exploratory and will not be used to guide treatment decisions.

10 ETHICAL, FINANCIAL, AND REGULATORY CONSIDERATIONS

This trial will be conducted according to the standards of Good Clinical Practice outlined in the ICH E6 Tripartite Guideline, and CFR Title 21 part 312, World Medical Association's Declaration of Helsinki, applicable government regulations, institutional research policies and procedures and local applicable regulatory requirement(s).

All potential serious breaches must be reported to Rhizen Pharmaceuticals SA immediately. A serious breach is a breach of the conditions and principles of GCP in connection with the study or the protocol, which is likely to affect, to a significant degree, the safety or physical or mental integrity of the subjects of the study or the scientific value of the study.

10.1 IRB/IEC Approval

The study protocol, ICF, IB, available safety information, patient documents, patient recruitment procedures (e.g., advertisements), information about compensation available to the patients and documentation evidencing the PI's qualifications should be submitted to the IRB/IEC for ethical review and approval if required by local regulations, prior to study start.

The PI/Rhizen and/or designee will follow all necessary regulations to ensure appropriate, initial, and ongoing, IRB/IEC trial review. The PI/Rhizen (as appropriate) must submit and, where necessary, obtain approval from the IRB/IEC for all subsequent protocol amendments and changes to the informed consent document. Investigators will be advised by Rhizen or designee whether an amendment is considered substantial or non-substantial and whether it requires submission for approval or notification only to an IRB/IEC.

Safety updates for Tenalisib will be prepared by Rhizen or its representative as required, for submission to the relevant IRB/IEC.

10.2 Regulatory Approval

As required by local regulations, Rhizen will ensure that all legal aspects are covered, and approval of the appropriate regulatory bodies obtained, prior to trial initiation. If required, Rhizen will also ensure that the implementation of substantial amendment to the protocol and other relevant trial documents happen only after approval by the relevant regulatory authorities. Safety updates will be prepared by the Rhizen or its representative as required, for submission to the relevant regulatory authority.

10.3 Insurance and Indemnity

Details of insurance and/or indemnity will be contained within the written agreement between the PI/site and Rhizen. Rhizen will reimburse the subject for all study-related injuries provided that the injury does not arise from the subject's misuse of the study drug or failure to follow the Investigator's instructions.

10.4 Financial Disclosure and Obligations

Principal Investigators and Sub-Investigators are required to provide financial disclosure information to allow Rhizen to submit the complete and accurate certification or disclosure statements required under Part 54 of Title 21 of the CFR. In addition, the Principal Investigator or Sub- Investigators must provide to the Sponsor a commitment to promptly update this information if any relevant changes occur during the course of the investigation and for 1 year following the completion of the study.

10.5 Informed Consent

Informed consent is a process by which a subject voluntarily confirms his or her willingness to participate in a particular trial, after having been informed of all aspects of the trial that are relevant to the subject's decision to participate. Informed consent is documented by means of a written, signed and dated informed consent form.

The informed consent form will be submitted for approval to the IRB/IEC that is responsible for review and approval of the trial. Each consent form must include all of the relevant elements currently required by the regulatory authorities or state regulations and national requirements. Translation of the informed consent form is allowed if necessary.

Before recruitment and enrollment into the trial, each prospective candidate will be given a full explanation of the trial. Once the essential information has been provided to the prospective candidate, and the investigator is sure that the individual candidate understands the implications of participating in this trial, the candidate will be asked to give consent to participate in the trial by signing an informed consent form. A notation that written informed consent has been obtained will be made in the patient's medical record. A copy of the signed informed consent form will be provided by the investigator to the patient.

If an amendment to the protocol substantially alters the trial design or the potential risks to the patients, the patient's re-consent to continue participation in the trial should be obtained.

10.6 Confidentiality

10.6.1 Patient Confidentiality

Confidentiality of patient's personal data will be protected in accordance with the Health Insurance Portability and Accountability Act of 1996 (HIPAA) and national data protection laws or specific country requirements, as applicable. HIPAA regulations require that, in order to participate in the trial, a patient must sign an authorization from the trial that he or she has been informed of following:

- a. What protected health information (PHI) will be collected from patients in this trial;
- b. Who will have access to that information and why;
- c. Who will use or disclose that information;
- d. The information collected about the research trial will be kept separate from the patient's medical records, but the patient will be able to obtain the research records after the conclusion of the trial;
- e. Whether the authorization contains an expiration date;
- f. The rights of a research patient to revoke his or her authorization.

In the event that a patient revokes authorization to collect or use his or her PHI, the investigator, by regulation, retains the ability to use all information collected prior to the revocation of patient authorization. For patients that have revoked authorization to collect or use PHI, attempts should be made to obtain permission to collect at least vital status (i.e., that the patient is alive) at the end of their scheduled trial period.

In compliance with ICH GCP guidelines and applicable parts of 21 CFR, it is a requirement that the investigator and institution permit authorized representatives of Sponsor, the regulatory authorities and the IRB/IEC direct access to review the patient's original medical records at the site for verification of trial-related procedures and data.

Measures to protect confidentiality include mentioning of only a unique trial number and initials will identify patients on the CRF or other documents that will be submitted to Rhizen. This information, together with the patient's date of birth, will be used in the database for patient identification. Patient names or addresses will not be entered in the CRF or database. No material bearing a patient's name will be kept on file by Sponsor. Patients will be informed of their rights within the ICF.

